Exclusion Criteria for Youth Participants. Exclusion criteria include not meeting the inclusion criteria or are overtly exhibiting symptoms of severe, untreated mental illness criteria we used successfully in our previous studies with homeless youth. Youth will be excluded if they do not meet the criteria for age (18-25 years old) or are not staying at the shelter or currently experiencing homelessness or unstable housing. Experiencing homelessness will be defined as having slept on the streets, in a place not meant for habitation, in a shelter, in a hotel/motel, or with someone where they cannot stay for more than 30 days (e.g., couch surfing). YEH may stay in emergency shelters or on the streets (e.g., parks and tent cities), in abandoned or vacant buildings or apartments, temporarily with friends, family, or acquaintances (i.e. “couch surfing”), or in motels¹⁰¹ and go to great lengths to stay hidden from the dangers of victimization.¹⁰ This broader definition of homelessness aligns with the McKinney-Vento Homeless Assistance Act of 1987, allows us to account for the transiency and instability of housing experienced by YEH, and increases the generalizability of the study findings. If youth are overtly having severe, untreated mental illness symptoms, they will be asked to come back at a later date and still be eligible for subsequent screening for enrollment.

All participants will have ongoing access to mental healthcare services through the onsite health clinic located at the CHT shelter. Should study staff become aware of a participant experiencing significant symptoms during the study, they will be connected immediately to onsite mental health treatment resources and removed from the study. Based on our initial pilot of *b*, where we had no incidences of significant symptoms, we do not anticipate this happening frequently.

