Recruitment. Given the inclusion criteria and site volume for the pilot, we expect to recruit 15 youth per arm (intervention and attention control) session for a total of 3 cohorts of 15 in each arm or 6 total groups. Based on what we've learned from previous studies with YEH, we will recruit 90 youth to deliver the intervention or control to at least 60 youth. Youth will be recruited primarily from Covenant House Texas (CHT), and homeless shelters and drop-in centers if additional recruitment sites are needed, to participate in the pilot. Youth who are eligible and enroll in the pilot study will complete a baseline survey, attend 5 90 minute sessions, complete very brief pre-post session surveys, as well as follow-up surveys immediately post-intervention and at 3 months post-intervention. Approximately 22% (n=20) of the pilot study participants will be recruited to also participate in a post-intervention exit interview. Participants will have the phone for the duration of the study. The intervention is informed by the Risk Amplification Model (RAM) and the Minority Stress Model (MSTM) and will be fully developed in Years 1-2 using a systematic intervention development process; Plan, Do, Study, and Act. In order to ascertain the feasibility and acceptability of the intervention (Aim 3), we will obtain participant feedback via exit interviews as well as quantitative implementation indicators (e.g., refusal rate, completion rates, and survey measures).

Inclusion/Exclusion of Service Providers. Key Informant Interview participants (n=12) and Expert Advisory Panel service provider members (EAP, n=8) will be health and social service providers for YEH recruited from local shelters (i.e., resident advisors, in-take specialists), drop-in centers (i.e., social workers, case managers), homeless healthcare clinics (i.e., nurses, mental health counselors, patient navigators), and the Homeless Youth Network (a network of YEH providers, of which [name] is an active member). Providers will be considered eligible if they are currently providing health or social services to YEH and are interested in participating in an interview or as a member of the Expert Advisory Panel. For those providers interested in the EAP, they will be considered eligible if they anticipate being able to meet for the regularly scheduled meetings at least 75% of the time.

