Youth Participants will include YEH aged 18-25 years recruited from CHT by the trained Research Coordinator (RC) and Research Assistant (RA) via group sessions introducing the study and by word of mouth from CHT staff. Very few youth under 18 years of age access services in Houston, TX. Using the approach successfully employed in our pilot project, study staff will describe the program and review a study summary and consent documents with interested individuals. Participating youth will provide written consent, witnessed by study staff. Staff will follow the intervention protocol for assessing eligibility, recording basic demographic information (e.g., age, gender identity, race/ethnicity, and sexual orientation) to assess for refusal bias. **Inclusion/Exclusion Criteria.** Youth will be eligible if they are between the ages of 18-25 and are accessing resources at the shelter during the recruitment phase. We will use a tiered eligibility screening method which we used in the pilot study, to assure that youth with a mental illness diagnosis, with non-severe symptoms who can perform activities of daily living and would otherwise be able to successfully complete the intervention, are not denied the opportunity to participate in the program. This tiered screening method is an essential adaptation for reaching YEH who, by nature, have high rates of mental illness, stress, and emotion dysregulation. To assess symptom severity that warrants delay in enrollment or exclusion, we will implement several exclusion criteria. Youth will be excluded if they do not meet the criteria for age (18-25 years old) or are not staying at the shelter or currently experiencing homelessness or unstable housing. If youth are overtly having severe, untreated mental illness symptoms they will be asked to come back at a later date and still be eligible for subsequent screening for enrollment. All participants will have ongoing access to mental healthcare services through the onsite health clinic located at the CHT shelter. Should study staff become aware of a participant experiencing significant symptoms during the study, they will be connected immediately to onsite mental health treatment resources and we will consult with the DSMB to see if it is connected to the study. If a participant contacts someone from the study team, we will follow the same procedure. Based on our initial pilot of *.b*, where we had no incidences of significant symptoms, we do not anticipate this happening frequently. **Key Informant Interview Participants** (n=12) will be current YEH health and social service providers recruited from local shelters (i.e., resident advisors, in-take specialists), drop-in centers (i.e., social workers, case managers), homeless healthcare clinics (i.e., nurses, mental health counselors, navigators), and the Homeless Youth Network (a network of YEH providers, of which [name] is a member). **Expert Advisory Panel** (n=10) will comprise 8 YEH service providers recruited from the Homeless Youth Network and 2 YEH between 18-25 years old. The group will meet by phone or in-person every other month for one hour during the study to provide input

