Enrollment and Data Collection Procedures. The RC and RA will recruit and enroll all participants. Once consented, the youth will take the baseline survey and receive their group assignment from the RC. A computerized randomization generator will be used. The RA will be blinded to group assignment and will conduct all data collection. For the purpose of this study, enrollment will be defined as completing consent, baseline survey, and at least one lesson of the intervention or control condition. Surveys will be completed by participants on iPads using REDCap. Participants will enter response data directly into the tablet so their answers will be private. In the case of electronic device failure, we will use back-up iPads and paper surveys and the RA will enter the responses into REDCap within 24 hours. We will use unique study IDs in the place of names to protect participant confidentiality. **Baseline and Follow-up Surveys.** Participating youth will complete surveys at baseline, immediate post-intervention, and at 3- and 6-months post-intervention. Surveys will take approximately 30 minutes to complete and will include items to measure mindfulness, perceived stress, emotion regulation, impulsivity, and mental health symptoms (see Table 2 for example measures and psychometric properties) and youth risk behaviors. We will also pilot self-report and app use to determine the most effective way to measure use of commercially available mindfulness apps. Data usage information will be gathered from mediation app on participants' phone. **Pre- and Post-Session Surveys.** Very brief pre- and post-session brief surveys will capture real-time stress, emotion regulation, positive and negative affect, mindfulness, impulsivity, and session feedback (post-session only) including likability of session content, delivery format, length, and delivery timeframe. These surveys will take approximately 5 minutes to complete prior to and immediately after each session. **Exit Interviews.** The RC will conduct individual or group exit interviews with 20 youth from the pilot study participants that will be audio-recorded and take about 30-45 minutes. We will randomly select participants from each of the 4-6 intervention cohorts to have equal representation by gender identity, age, and study group. We will elicit participant feedback on study procedures, intervention acceptability, delivery methods and strategies, barriers and facilitators of

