session participation, mindfulness skills practice, measures completion, and overall experience with the intervention and the study. While the exit interview guide will be finalized during YR-1 with the assistance of the HYWG, we anticipate querying the participants about: 1) what the participant thought of the number and type of questions asked in the baseline, pre-post session, and initial follow-up survey, 2) thoughts on the intervention sessions (e.g., content, length, delivery mode, frequency/spacing, perceived impact), and 3) any other comments about the intervention or study procedures including a comparative analysis¹⁸⁰ of the commercially available mindfulness apps. Participants will receive an additional \$10 gift card for a local restaurant or grocery store for completing the exit interview.

Table 3. Feasibility and Acceptability Benchmarks

Construct	Measure	Benchmarks
Recruitment feasibility	# screened & enrolled/mo; time delay from screening to enrollment; average time to enroll sufficient class size; appropriateness of exclusion criteria screening process	Enroll 50% of screened and eligible participants; <2-week delay from screening to enrollment; <2 weeks to enroll sufficient class size; <5% inappropriate exclusion/inclusion
Retention feasibility	3- and 6-mo follow-up survey completion; compare intervention vs. control group	At least 50% retained at 3 and 6-mo; <15% group retention differential
Treatment adherence	Attend all sessions; perform the intervention; complete study measures	At least 50% of participants in each cohort will attend at least 3 of 5 scheduled group sessions ^{108,164}
Treatment delivery fidelity	Session delivery fidelity checklist	At least 70% of each session content is completed
Completeness of assessment data	Data from surveys, focus groups, and key informant interview are complete and intact	Less than 50% data loss or incompleteness
Acceptability	Credibility/expectancy questionnaire ¹⁸¹	Average score of >30

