1. Serious events include any event or condition that is life threatening, results in a hospitalization, cancer or a physical or cardiac event serious enough to require medical attention. These events may be:
 - a. Fatal
 - b. Life threatening
 - c. Permanently disabling
 - d. Required or prolonged hospitalization (Admission—not ER visit)
 - e. Overdose
 - f. Significant hazard to patient
2. Non-Serious events includes all other events.

In addition, follow-up face-to-face visits at 3 and 6 months will include a query of subjects on whether they had “any serious health events that caused them to seek medical attention within the past 3 months,” and if any of these resulted in “hospitalizations overnight.” Details of these events will be recorded. All adverse reactions noted by any of the team members will be immediately reported to the principal investigator, the UTHealth IRB, Data Safety and Monitoring Board, and NCCIH. All adverse events will be reviewed monthly by the research team and annually by the monitoring board. Also, in keeping with NIH guidelines, minority status and gender will be included in these reports to allow for detection of differential effects.

Data and Safety Monitoring Plan. This study is considered to constitute minimal psychological and physical risk and no legal or social risks. The risks are minimal since educational interventions generally promote good health, not endanger it. Our eligibility criteria are established to exclude individuals for whom the study procedures are not appropriate. We also will screen subjects directly using validated and reliable items for collecting information on co-morbidities such as unresolved serious mental illnesses or low literacy. Using this multi-gated approach, we should be able to effectively screen out any individuals for whom this intervention is contraindicated. All health-related occurrences will be recorded and regularly reviewed by the research staff.

A few potential minimal risks to subjects exist: breach of confidentiality or normal risks associated with having a phone. Breach of confidentiality is not believed to present any significant risk given the data protections described above. However, to mitigate this risk we have outlined steps we will take to protect confidentiality in the Human Subjects sections

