Participant Discomfort. Mindfulness practices, survey questions, and exit interviews might create awkwardness or discomfort. A potential risk in participating in the proposed research is becoming more aware of and/or reporting past events, current circumstances, thoughts and feelings, and risk behaviors that may make participants feel uneasy. Our experienced research staff will receive an additional 16 hours of training before initiating recruitment for this study to assure that all protocols and procedures are followed. Our staff have worked on several studies with homeless youth under the supervision of [name]. If new staff are hired during the study, they would receive a minimum of 40 hours of project training in addition to the university-level and Human Subjects training. Research staff will have ongoing supervision in how to handle awkwardness, embarrassment, or discomfort. Participants can choose whether to be in the study or not. They may withdraw at any time without consequences of any kind. They may also refuse to answer any questions they do not wish to answer and still remain in the study. It is possible that there may be occasions when study participants exhibit stronger and more serious signs of emotional distress; we may encounter individuals who express suicide intent, have psychiatric emergencies, or exhibit other indicators of acute distress. Research staff will be trained to identify signs of acute distress or suicidal ideation and trained how to respond to them. With respect to the assessments, we will emphasize to research staff that if a participant becomes upset, they should be offered the option of discontinuing without penalty (i.e., still receiving payment) or continuing at a later time after a break. Further, the computer-assisted survey administration limits participant exposure to potentially sensitive items. For example, participants who have not engaged in a certain risk behavior, such as substance use, are not exposed to more detailed questions about use. Participants will also be informed that they may skip any item that makes them feel uncomfortable. In the event of any acute emotional distress, research staff will remain with the participant until s/he is no longer distressed.

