The CHT shelter where the intervention sessions will be conducted has 24-hour staff trained in managing acute episodes of distress or even psychosis. We will follow the protocols of the shelter, who have over 30 years of experience with homeless youth. Additionally, the shelter has a fully functional Federally Qualified Healthcare Center on the premises with clinical psychologists and a psychiatrist on staff. Individuals who wish to pursue follow-up care will also be given a referral list specifically tailored to the individual's request. We will have prepared referral lists for perpetrators and victims of abuse as well as for other psychological problems. At the end of each assessment, all participants will be offered a list of relevant, local referrals. We will not be asking about suicidal ideation, so it is unlikely that we will have to deal with acute suicidal ideation. However, anyone having direct involvement with the participants will be fully trained by the PI in procedures for assessment and intervention in cases where suicidal ideation is expressed. Research staff will be instructed to immediately contact shelter staff to implement shelter protocols on suicidal ideation and to contact the PI and take appropriate clinical action in these circumstances to assure participant and staff safety including referral to another level of clinical care. As well, recruitment will take place in shelters and drop-in centers staffed by trained clinical social workers, case managers, and healthcare providers. RAs will be able to notify recruitment site staff and facilitate implementation of protocols for care in cases of acute distress. Experienced supervisors

and [name] will be available for immediate consultation in the event of encountering an unexpected acute psychological problem; and as part of their training, research staff will be made familiar with referral resources and procedures for local psychological, social service, and other emergency care needs.

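### Participants with significant symptoms are removed from the study, which as written ends their 3- and 6-month follow-up; stopping sessions and keeping follow-up would be a better rule at little cost

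*Combined protocol and SAP*

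**What the plan says.** Three sections of the combined protocol and SAP deal with staff learning that a participant has significant symptoms during the study.

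- Exclusion Criteria for Youth Participants (Study Population): the participant is "connected immediately to onsite mental health treatment resources and removed from the study". The DSMB is not mentioned.
- Youth Participants, Inclusion/Exclusion Criteria (Study Procedures): same trigger and same referral, then "we will consult with the DSMB to see if it is connected to the study". Removal is not mentioned.
- Adverse Event Reporting (Data and Safety Monitoring): the same trigger, referral and DSMB step. Again removal is not mentioned.

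Participant Discomfort covers neighbouring situations and does not mention removal either. For participants who become upset during an assessment, "they should be offered the option of discontinuing without penalty (i.e., still receiving payment) or continuing at a later time after a break". Where suicidal ideation is expressed, staff involve shelter staff and the PI and "take appropriate clinical action in these circumstances to assure participant and staff safety including referral to another level of clinical care".

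Two later measurements depend on continued participation. Table 3 measures retention by completion of the 3- and 6-month surveys, with the benchmark "At least 50% retained at 3 and 6-mo; <15% group retention differential". Adverse Event Reporting adds that "follow-up face-to-face visits at 3 and 6 months will include a query of subjects" about serious health events and overnight hospitalizations.

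**The concern.** On its ordinary meaning, removal from a study ends all study contact, including follow-up visits. No section limits it to the sessions. Two things then go missing for the youth concerned.

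The first is safety information. The protocol accepts under Risk to Human Subjects that mindfulness practice may itself cause distress. Adverse Event Reporting asks the team and the board to judge whether each event is attributable to the intervention. What happens to a symptomatic participant over the next months bears on that judgement, and the structured query at 3 and 6 months is where it would be collected.

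The second is outcome data. The surveys measure stress, emotion regulation and mental health symptoms. A participant removed because of mental state has outcomes that are missing for a reason tied to what is being measured, so the descriptive means at later visits would leave out some of the most distressed youth. The pilot also sets out to learn whether its criteria identify and exclude youth who cannot safely take part, and these are the cases that inform that question.

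**Working it through.** **Step 1: set the three rules side by side.**

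| Section | Refer | Consult DSMB | Remove |
|---|---|---|---|
| Exclusion Criteria for Youth Participants | yes | not mentioned | yes |
| Youth Participants, Inclusion/Exclusion Criteria | yes | yes | not mentioned |
| Adverse Event Reporting | yes | yes | not mentioned |

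Staff following the first section would remove the participant. Staff following either of the others would not be told to.

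**Step 2: what removal takes away and what it leaves.** It takes away the remaining surveys and the health-event query. It leaves the record of the triggering event, which is logged and reported to the PI, the IRB, the DSMB and NCCIH (Adverse Event Reporting; Role of the PI and Investigative Team).

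**Step 3: size of the effect on retention.** The plan gives no removal rate, so there is no stated figure to reproduce. The effect per removal can be bounded.

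Inputs:
- n, participants per arm. It is 90/2 = 45 if all recruited youth count (Sample Size for Pilot RCT, equal randomization). It is nearer 60/2 = 30 if the base is those who receive the sessions: "enrollment will be defined as completing consent, baseline survey, and at least one lesson of the intervention or control condition" (Enrollment and Data Collection Procedures) and "we will recruit 90 youth to deliver the intervention or control to at least 60 youth" (Recruitment).
- r, the chance that a removed youth would otherwise have been retained. This is an assumption, from 50% (the Table 3 benchmark) to 100%. Values of 80% and 85% correspond to the projected drop-out of 15-20% (Role of the PI and Investigative Team).

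The ratio 60/90 is not used for r. It describes getting through the sessions, not retention at 3 or 6 months, and it is already what turns 45 into 30.

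Formulas:
- Points lost in the arm per removal = 100 × r/n.
- Removals needed to reach a 15-point differential, if all fall in one arm and the arms are otherwise equal = 0.15 × n/r, rounded up.

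| r | Points per removal, n = 45 | Removals to reach 15 points, n = 45 | Points per removal, n = 30 | Removals to reach 15 points, n = 30 |
|---|---|---|---|---|
| 50% | 1.1 | 13.5, so 14 | 1.7 | 9.0, so 9 |
| 80% | 1.8 | 8.4, so 9 | 2.7 | 5.6, so 6 |
| 85% | 1.9 | 7.9, so 8 | 2.8 | 5.3, so 6 |
| 100% | 2.2 | 6.75, so 7 | 3.3 | 4.5, so 5 |

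Reaching the differential would take 7 to 14 removals with 45 per arm, or 5 to 9 with 30, all in the same arm. The earlier pilot had none. The 50% retention benchmark could turn on a single removal only if an arm sat almost exactly on it. For example, 23/45 = 51.1% would fall to 22/45 = 48.9%.

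**The case against.** The strongest reply is that removal is a defensible clinical choice and that little hangs on it. Severe, untreated symptoms already bar entry, so stopping when significant symptoms emerge is broadly consistent with the entry rule. Survey questions can themselves upset participants. The affected youth is connected at once to onsite care, in a shelter with 24-hour trained staff and an onsite health center with psychologists and a psychiatrist. Participants are told to call the study number about emergencies, and the team reviews adverse events monthly.

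Most of this stands, and it limits the point to a small one. It supports stopping sessions, and sparing a participant a survey when a clinician sees a reason. It does not support ending follow-up for every such participant as a rule.

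Four stronger readings are tempting, and the documents do not support them.

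- *The sections contradict each other.* They differ, but a team could refer, remove and consult without breaking any of them. Silence on removal in two places does not forbid it.
- *The safety event itself is lost.* It is not. It is logged, classified and reported. What could be lost is the structured query at two later visits.
- *Removals would fall unevenly and bias the comparison or breach a benchmark.* Nothing in the documents suggests more removals in one arm. The analyses are frequencies, percentages, means and effect-size estimates, with no inferential testing, and the counts in the table above are far from what is expected.
- *Removed youth could be dropped from the retention denominator.* On a plain reading, an enrolled youth who completes no later survey counts as not retained, and nothing authorises taking them out. The plan does not say this in so many words, but the gap is narrow.

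Nor is the point that removal lacks a definition. That alone would be missing detail, and the consent form, which might say more, is not in the text reviewed. The point is that the rule as written is worse than an easily available alternative.

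**Conclusion.** The point holds as a low-severity, cheap improvement. As written, the Exclusion Criteria section ends structured safety and outcome follow-up for the participants in whom it is most informative, and two other sections with the same trigger do not ask for this. The likely number affected is very small, and no Table 3 benchmark consequence is expected.

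The conclusion rests on reading removal in its ordinary sense. If the sponsor means only that sessions stop, little is lost and the change amounts to wording. The retention figures rest on the assumed range for r, on the two possible arm sizes, and on counting removed youth as not retained.

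**What to change.** Use one rule in the three sections that carry the trigger:

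- Refer to onsite care, consult the DSMB, and stop sessions if clinically indicated.
- In the Exclusion Criteria section, replace removal from the study with stopping sessions.
- Still offer the remaining surveys and the 3- and 6-month health-event query, unless the participant withdraws consent or the treating clinician advises against it.
- Keep these youth in the Table 3 denominators, and report their number and the reasons by arm.

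The cost is protocol wording in three places, a few extra follow-up contacts, and possibly a slightly less favourable adherence or retention figure.
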